## Evaluation of Wall Shear Stress and Neointimal Healing Following Percutaneous Coronary Intervention of Angulated Vessels with Resolute® Integrity™Zotarolimus Eluting Coronary Stent Compared to XIENCE XPEDITION® Everolimus Eluting Coronary Stent (SHEAR-STENT Study)

## Rationale

After approval of the Resolute Integrity® Zotarolimus drug-eluting stent (R-ZES) in February 2012 by the U.S. Food and Drug Administration, it and the Abbott Vascular's XIENCE XPEDITION® Everolimus drug-eluting stent (X-EES) are expected to be market share leaders. A recent head-to-head trial (Resolute All Comers Trial) comparing these two stents demonstrated non-inferiority of R-ZES to X-ESS for the primary endpoint of target lesion failure at 12 months (8.2% and 8.3%, respectively, *p*< 0.001 for non-inferiority) with a non-significantly higher rate of stent thrombosis of R-ZES compared with X-EES (2.3% vs. 1.5%, respectively; *p* = 0.17). The non-inferiority of the R-ZES to X-EES has been reconfirmed in real-world patients by the TWENTE Trial. While such studies provide significant empirical data on the clinical performance and safety of the new R-ZES compared with X-ESS, they do not offer insight into the possible mechanisms relating to early and late stent healing that can drive clinical adverse outcomes.

Although drug-eluting stents (DES) have significantly reduced restenosis rates, concerns of late stent thrombosis (LST) and timing of re-endothelialization persist. Numerous mechanisms have been implicated in the cause for LST, including several aspects of stent design. While the elution characteristics of the R-ZES are similar to X-ESS, the BioLinx tri-polymer coating of R-ZES may be more biocompatible than the X-EES polymer and preclinical porcine models have demonstrated reduced inflammatory scores with R-ZES. Furthermore, the altered biomechanical environment post-stenting (e.g., hemodynamics, arterial straightening) can significantly affect the recovery time of endothelial structure and function.

The deployment of a stent in an artery significantly affects the near-wall flow patterns, as well as the overall flow patterns in the artery. Specifically, the protrusion of the stent strut into the lumen results in flow separation and the formation of recirculation zones or eddy currents both proximal and distal to each stent strut. These non-physiologic flow characteristics near stent struts persist until re-endothelization and neointimal tissue growth occurs. The degree to which the flow patterns are disrupted depends strongly on the stent design.

Computational fluid dynamics (CFD) techniques have been employed to investigate the hemodynamic alterations following stent deployment as they allow for accurate information on flow parameters [e.g., wall shear stress (WSS), velocity, pressure]. Duraiswamy and colleagues quantified WSS values near stent struts in four commercially available stents. Results indicated that stent designs whose struts were aligned perpendicular to the flow direction resulted in much lower WSS values and greater flow disturbances than designs that did not have these design characteristics. Furthermore, stent designs whose struts were aligned primarily in the axial direction (i.e., the direction of blood flow) disturb flow the least. Examination of the R-ZES design reveals a continuous wire that is molded into a sinusoidal wave and wrapped in a helical pattern and laser-fused at certain points. This allows significantly more struts to be aligned in the axial direction than the X-EES design.Furthermore, the conformability of the R-ZES may cause less vessel straightening and less plaque prolapse, leading to more physiologic shear stress compared to X-EES. *Thus, we* 

hypothesize that R-ZES will result in less disturbed flow and more physiologic WSS at the stent edges compared with the X-EES design and promote more complete tissue coverage within the stent.

## **Specific Aim:**

The aim of this proposal is, in patients undergoing PCI to angulated coronary arteries, to:

- 1) To calculateOCT-derived WSSwithin R-ZES and X-EES stents and relate differences in regional in-stent WSS to neo-intimal tissue coverage assessed by OCT at one year.
- 2) To calculate/VUS-derived WSSat the R-ZES and X-EES stent edges and relate differences in regional WSS at stent edges to change in plaque areaat one year.

## **Hypotheses:**

In patients undergoing PCI to angulated coronary arteries:

- With a conformable stent design that is more conducive to physiologic flow characteristics, the R-ZES stent will result in less vessel straightening and less plaque prolapse compared to X-EES. This would result in fewer lowWSS areas within the stent that, in turn, would lead to less neo-intimal tissue coverage.
- R-ZES will result in less straightening of vessel at the stent edges compared with X-EES, yielding fewerlow WSS segments which, in turn, will result in less plaque area at the stent edges at one year.

## Design

One hundred twenty six patients from participating US and international study sites *Emory University* Hospital (Atlanta, GA), Hospital Clinico San Carlos (Madrid, Spain), Seoul National University College of Medicine (Seoul, S. Korea), Keimyung University Dongsan Medical Center (Daegu, S. Korea), Ulsan University Hospital - University of Ulsan College of Medicine (Dong-gu, S. Korea), Wakayama Medical University (Wakayama, Japan), Kobe University (Kobe, Japan), Clinical Center of Serbia (Belgrade, Serbia), Nanjing Medical University (Nanjing, China), Samsung Medical Center (Seoul, S. Korea), Kyushu Medical Center (Fukuoka, Japan), Teikyo University (Tokyo, Japan), New Tokyo Hospital (Tokyo, Japan), University of Latvia, (Riga, Latvia)undergoing PCI to angulated coronary vessels will be randomized to stent implantation with either the R-ZES or X-EES in a 1:1 ratio. Allocation of stent types will be blinded to patients. Prior to stent deployment, IVUS and OCT will be performed to assess the baseline plaque composition. After successful stent deployment, post-stent OCT and IVUS will be performed to assess the adequacy of stent deployment. Using OCT, IVUS, and angiographic data, computational fluid models will be performed off-line to measure regional WSS. Patients will then be followed on optimal medical therapy including dual anti-platelet therapy for one year. They will also receive a follow up phone call by study staff at 6 months to assess their clinical status and medication compliance. At 1 year follow-up, patients will return to the cardiac catheterization laboratory for repeat angiography, OCT, and IVUS. Of the total n=630 subjects projected to be enrolled, 80% (n=504) is anticipated to screen fail based on the predefined inclusion criteria. Subsequently we anticipate n=126 subjects to complete baseline evaluation. A 20% drop out rate for the 1-year follow-up invasive evaluation has been considered reducing the total number of subjects completing the follow-up to n=100. Patients will be stratified on the basis of whether they have diabetes or not, as diabetic patients have long been recognized as a complex PCI cohort and associated with an increased risk of major adverse cardiovascular events, including death and myocardial infarction.

Figure 1: Schematic of Study Design. CFD: computational fluid dynamic simulations, IVUS: Intravascular Ultrasound, OCT: Optical Coherence Tomography, PCI: percutaneous coronary intervention, SIHD: stable ischemic heart disease

Fig.2: Flow chart of the SHEAR-STENT Study

### Methodology:

#### **1.** Angiography and Percutaneous Coronary Intervention

Patients will undergo routineangiography (bi-planar views if available) and stent deployment per standard of care.

### 2. Angiographic assessment of angulation

Angulation is the angle created by the intersection of two tangential lines at the beginning and end of an index coronary segment with the angiogram frozen in end-diastole. In this study, we define an angulated vessel as one with ≥30degrees bend (Figure 3). When the angulation is clearly >60 degrees, a visual assessment by the investigator will suffice for enrollment. However, for angles <60 degrees the angiographic image is frozen in end diastole in the control room and printed on paper. Subsequently, 2 tangential lines are drawn on the vessel at the proximal and distal edge of the lesion and the intersecting angle measured with a protractor. In cases where the affected artery/stent has more than one curvature (assumes an "S" shape, instead of variations of a "C" shape), the

Figure 3: Angulation

higher degree of angulation will be analyzed. Stents that overlap or are in very close proximity to each other with a gap of less than 5 mm will be assigned to the same

coronary lesion.

#### **3. Intravascular Imaging**

#### 3.1. Data Acquisition

Optical coherence tomography (OCT) and Intravascular ultrasound (IVUS) will be performed at baseline to assess plaque burden prior to and after stent deployment as well as to evaluate stent expansion and stent apposition. OCT and IVUS will be repeated at one year follow-up to evaluate neo-intimal tissue coverage within the stent and change in plaque area at the stent edges. IVUS analysis will be performed with a motorized pullback at 0.5 mm/s. Following IVUS, OCT will be performed with a commercially available system (C7-XR™ OCT Intravascular Imaging System, St. Jude Medical). The OCT catheter will be positioned distal to the region of interest and automated pullback will be performed at 20 mm/s while the blood is removed by the continuous power injection of iso-osmolar contrast through the guiding catheter.

#### 3.2. Data Analysis

Both stent platforms are FDA approved and clinically utilized in the United States and internationally. This trial is not powered to detect clinical outcome difference between the two stent platforms but rather enhance our understanding of the relationship between biomechanics and stent healing in these angulated vessels. We therefore do not think this trial will be discontinued and hence do not plan to perform an interim analysis.

Offline, manual detection of lumen area, stent area, vessel area(external elastic membrane) and the media-adventitia interface will be performed for each IVUS cross-section from baseline and follow up examinations. Cross sections with rotational distortion artifacts and severe calcifications will be excluded from the analysis. Plaque area and plaque burden will be measured at baseline and follow up for every IVUS cross-section from the pullback run. Baseline and follow-up IVUS cross-sections will be compared, reviewed and co-registered based on a reproducible index side branch atthe distal end of the target segment. Changes in external elastic membrane, lumen area, plaque burden and plaque area, and fourplaque tissue components defined by IVUS-virtual histology(necrotic core, dense calcium, fibrous tissue, and fibrofatty tissue) will be calculated as follow-up values minus baseline values for each IVUS segment. The 5 mm segments proximal and distal to the stent edges will be defined and analyzed with IVUS. Change in plaque area at the stent edges (secondary IVUS endpoint) will be calculated from the change in plaque area in the 5 mm proximal and distal segments as described above.

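### The stent-edge plaque endpoint does not name its baseline IVUS scan, and its arm comparison has no stated covariates; naming the scan and adjusting is a low-cost, possible precision gain

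*Combined protocol and SAP*

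**What the plan says.** All references are to the combined protocol and SAP.

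- **Endpoint.** Secondary Endpoints, part B (Stent Edge), lists change in plaque area at follow-up as the efficacy measure. Section 3.2 derives it: "Change in plaque area at the stent edges (secondary IVUS endpoint) will be calculated from the change in plaque area" in the proximal and distal 5 mm segments. Changes are "calculated as follow-up values minus baseline values for each IVUS segment".
- **Two scans at the index procedure.** Design: "Prior to stent deployment, IVUS and OCT will be performed to assess the baseline plaque composition". After deployment, "post-stent OCT and IVUS will be performed to assess the adequacy of stent deployment". Section 3.1 says that imaging at baseline serves "to assess plaque burden prior to and after stent deployment".
- **Wording that points to a scan after deployment.** Section 3.2 has manual tracing of lumen area, "stent area, vessel area(external elastic membrane) and the media-adventitia interface will be performed for each IVUS cross-section from baseline" and follow-up. It also says: "The 5 mm segments proximal and distal to the stent edges will be defined and analyzed with IVUS". Baseline and follow-up frames are "co-registered based on a reproducible index side branch" at the distal end of the target segment.
- **Analysis.** Statistics chooses a t-test or U-test according to distribution and spread. It names multilevel regression at patient, arm and lesion level and lists no covariates for any endpoint. Design says that patients are stratified by diabetes status, but Statistics does not take the stratum up.
- **Aim 2.** Specific Aim relates wall shear stress at the stent edges to the change in plaque area at one year, which is the same variable.

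**The concern.** Two analysts following this text could compute different endpoints. Change from the pre-deployment scan includes whatever the procedure did to edge plaque. Change from the post-deployment scan covers only the following year. Hypotheses expects the two stents to straighten the vessel differently at the edges, so an acute difference between arms cannot be ruled out. If the scan is chosen once data are in hand, the choice is open to discretion on a named efficacy endpoint, and it also sets the outcome of Aim 2.

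Separately, subtracting baseline fixes its coefficient at 1. A model that estimates the coefficient is, apart from a small cost in degrees of freedom, at least as precise and often more so. The trial collects the edge plaque values and the diabetes status, so leaving them out of the arm comparison may waste information.

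**Working it through.** **1. The plan's own figure.** The only sample-size calculation concerns tissue coverage volume. The difference is 22 − 14.68 = 7.32 mm³. The pooled variance from the quoted SDs (11.6 with 30 patients, 14.4 with 28) is (29 × 11.6² + 27 × 14.4²)/56 = 169.66, so the SD is 13.03. Then n = 2 × (1.960 + 0.842)² × 169.66/7.32² = 49.7, or 50 per group. Allowing for 20% dropout, 50/0.8 = 62.5, so 63 per group and 126 in total. The figures reproduce. They say nothing about edge plaque, for which the plan gives no SD, correlation or power.

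**2. Which scan?** Design attaches the word baseline to plaque composition on the pre-deployment scan, and section 3.2 subtracts composition by the same rule as plaque area. Yet section 3.2 also traces stent area on baseline frames and places the segments by the stent edges, which exist only after deployment. The text supports either reading.

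**3. Does the choice matter?** Suppose (assumed) that the arms differ in edge plaque by 0.3 SD straight after deployment and by 0.3 SD at one year. The expected difference in change is 0.3 − 0 = 0.30 from the pre-deployment scan and 0.3 − 0.3 = 0.00 from the post-deployment scan. Simulation with 50 per arm gave 0.30 and 0.00. Adjusting for the post-deployment value, with an assumed correlation of 0.7 with follow-up, gives 0.3 − 0.7 × 0.3 = 0.09, which is neither quantity.

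**4. Pre-deployment scan as baseline and as covariate.** Let r be the correlation of baseline with follow-up and k = SD(follow-up)/SD(baseline). The variance ratio, adjusted over raw change, is k²(1 − r²)/(1 + k² − 2rk), which is (1 + r)/2 when k = 1.

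| r (assumed) | k = 1 | k = 1.25 |
|---|---|---|
| 0.5 | 0.75 | 0.89 |
| 0.7 | 0.85 | 0.98 |
| 0.8 | 0.90 | 1.00 |
| 0.9 | 0.95 | 0.95 |

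At k = 1 and r = 0.5, 0.7 and 0.9, the standard error falls by 13.4%, 7.8% and 2.5% (1 minus the square root of the ratio).

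**5. Post-deployment scan as baseline, pre-deployment plaque added as covariate.** With equal SDs, let a = corr(pre, post), b = corr(pre, follow-up) and r = corr(post, follow-up). The variance of change is 2(1 − r) and its covariance with pre is b − a, so the ratio is 1 − (b − a)²/[2(1 − r)].

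| a, b, r (assumed) | Ratio |
|---|---|
| 0.9, 0.85, 0.9 | 1 − 0.0025/0.2 = 0.99 |
| 0.8, 0.75, 0.8 | 1 − 0.0025/0.4 = 0.99 |
| 0.9, 0.65, 0.7 | 1 − 0.0625/0.6 = 0.90 |
| 0.9, 0.6, 0.7 | 1 − 0.09/0.6 = 0.85 |
| any a = b | 1.00 |

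**6. Two edges per patient.** The formulas treat one value per patient. A simulation of the edge-level model with a patient effect used 50 per arm, a between-edge correlation of 0.4, 15 diabetic patients per arm and a 0.3 SD diabetes shift, all assumed. Step 4 at k = 1 and r = 0.5, 0.7 and 0.9 gave 0.74, 0.85 and 0.96. The first four rows of step 5 gave 1.00, 1.00, 0.90 and 0.85. At a = b = r = 0.7 the ratio was 1.005, the small cost of an idle covariate. The mean estimates stayed at zero, as they should with no true effect.

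**The case against.** - **The text may already imply the post-deployment scan.** Tracing stent area and locating stent edges both need a deployed stent, and the mechanistic edge endpoints are stated after PCI. That is a fair reading. It is not decisive, because Design ties baseline plaque composition to the earlier scan. The design and endpoint figures are not visible in the text reviewed, so a clarification there can be neither confirmed nor excluded.
- **Covariates are a matter of preference.** Raw change is valid, this is a secondary endpoint with no power target, and the multilevel models already named could carry covariates. All of this stands. It limits the point to an improvement in precision that needs only to be written down.
- **The gain is assumed and may be nil.** This also stands, most of all for the post-deployment reading. There the extra covariate requires locating the edges on the earlier pullback, a step that no section describes for plaque area. Its value also depends partly on where the assigned stent ends. Raw change from the pre-deployment scan shares that last weakness.

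A reader might infer that unadjusted change is biased. Under randomisation the documents do not support that. With 20% dropout planned for, adjustment could also reduce bias if dropout depends on baseline plaque, but nothing in the plan shows that it does. A reader might also infer that Aim 2 is untouched. The arm-comparison covariates leave it alone, but the unnamed scan does not, since Aim 2 uses the same change.

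**Conclusion.** The point holds as a definition gap plus a possible gain in precision. The subtracted scan is not named, and the two candidates answer different questions if the stents differ acutely at the edges. The arm comparison has no stated covariates, not even the stratification factor.

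With the pre-deployment scan as both baseline and covariate, the variance ratio runs from 0.75 to 0.95 for r from 0.5 to 0.9 with equal SDs, and reaches 1.00 at k = 1.25 and r = 0.8. These ratios do not carry over to the post-deployment reading, where an added pre-deployment covariate gives about 0.85 to 1.00. Every ratio rests on assumed correlations and SDs. The documents also give no basis for sizing the gain from the diabetes term. The primary endpoint and the sample size are not affected.

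**What to change.** 1. **Section 3.2:** add one sentence naming the IVUS scan that defines baseline for the edge endpoint. State that Aim 2 uses the same change.
2. **Statistics:** make the arm comparison of edge plaque change the multilevel model already named, with a patient effect joining the proximal and distal edges and the diabetes stratum as a covariate. Report the adjusted difference with its 95% CI beside the raw change.
3. **If the pre-deployment scan is baseline:** add that edge plaque area as a covariate. Taking follow-up or change as the outcome then gives the same arm coefficient.
4. **If the post-deployment scan is baseline:** keep change from that scan as the outcome, with the patient effect and diabetes stratum. Treat pre-deployment edge plaque as an optional covariate. Do not substitute follow-up area adjusted only for the pre-deployment scan: this brings procedural effects into the comparison and can lose precision. At the first setting in step 5 its variance ratio is (1 − 0.85²)/(2 × 0.1) = 1.39.

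The cost is SAP wording and about two degrees of freedom, with no new imaging. Under item 3 the endpoint itself already requires the edges to be found on the pre-deployment pullback. Under item 4 that is extra manual reading, needed only if the optional covariate is used; the side-branch landmark in section 3.2 could serve for it.

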#### 4. Wall Shear Stress Calculations

Computational fluid dynamic (CFD) simulations to calculate WSS values have been used extensively and validated in our laboratory. Following angiographic, IVUS and OCT acquisition, 3-dimensional (3D) coronary geometries will be reconstructed by determining the location of the OCT transducer during pullback by using the corresponding angiographic projections. The 3D reconstructed catheter core serves as the stem on which to rebuild the 3D geometry. Following image adjustment due to rotation, each frame is aligned perpendicular to the catheter core. Lumen boundary points for each frame will be determined connected by spline curves to connect consecutive images. The geometry is smoothed, meshed, and imported into the commercial solver (Ansys, Inc., Canonsburg, PA), which employs the finite volume method for solving the Navier-Stokes equations. Velocity profiles will be applied at the inlet, traction-free boundary conditions are applied at all outlets, and a no-slip boundary condition (v = 0) is applied at the wall. The fluid (blood) is assumed to be an incompressible Newtonian fluid, which is valid under the pulsatile, moderate Reynolds number flow conditions in coronary arteries. WSS values are determined as a function of time in the cardiac cycle and the evaluation is highly reproducible.

Nodal WSS values will be extracted from the area of interest (i.e., lesion/stented region and stent edges) of computational models at pre- and post-stenting. The stented region and 5-millimeter (mm) segments of the proximal and distal edges will be divided into 1- mm segments and WSS values will be spatially and temporally averaged. Low WSS will be defined as <10 Dynes/cm^2. Corresponding regions between the pre-and post-stenting models for a given patient will be examined to assess alterations in WSS following stent implantation. Arterial straightening will be assessed by examination of the OCT-derived coronary reconstructions. Following reconstruction, centerline data will be examined to quantify vessel curvature, average cross-sectional area, maximum/minimum/average lumen diameters, and vessel volume will be calculated.

### **Patient Selection**

Patients planned to be admittedfor coronary angiography and percutaneous coronary artery revascularization procedure should be screened for trial eligibilityby a member of the research team previously trained to the protocol. The investigator or designee will explain the nature and scope of the trial, potential risks and benefits of participation, and answer all questions. Subjects must consent to participate in the study and may withdraw their consent at any time without any penalty or loss of benefit.

### Patient Inclusion:

- 1. Patient must be 30 to 80 years old
- 2. Severe coronary lesion in a vessel with  $\geq$  30° angulation requiring PCI
- 3. Lesion treatable by a *single* Resolute Integrity or Onyx or Abbott Xience Xpedition or Sierra coronary drug eluting stent.
- 4. Patients with stable ischemic heart disease or acute coronary syndrome undergoing clinically PCI.

